## 4. OBJECTIVES

### 4.1. Primary Objective

*Immunogenicity*

*Persistence*

At 2, 3, 4, 5, 6 years after booster vaccination of children with MenACWY-TT or *Meningitec*

- To evaluate the persistence of meningococcal antibodies in terms of the percentage of subjects with rSBA antibody titres  $\geq 1:8$  for each of the four serogroups.

### 4.2. Secondary Objective

*Immunogenicity*

*Persistence*

At 2, 3, 4, 5, 6 years after booster vaccination of children with MenACWY-TT or *Meningitec*

- To evaluate the persistence of meningococcal antibodies in terms of the percentage of subjects with rSBA titres  $\geq 1:128$  and GMTs and hSBA titres  $\geq 1:4$  and  $\geq 1:8$  and GMTs for each of the four serogroups.

*Safety*

- To describe serious adverse events (SAEs) related to vaccination and any event related to lack of vaccine efficacy (ie, meningococcal disease) from the subject's last visit in study MENACWY-TT-048 EXT: 039 Y2, 3, 4, 5 (112036) up to each yearly visit in the current study in a retrospective manner.

## 5. ENDPOINTS

### 5.1. Primary Endpoints

- Persistence of antibodies with respect to components of the investigational vaccine, 2, 3, 4, 5, 6 years after booster vaccination:
  - rSBA-MenA titres  $\geq 1:8$ .
  - rSBA-MenC titres  $\geq 1:8$ .
  - rSBA-MenW-135 titres  $\geq 1:8$ .
  - rSBA-MenY titres  $\geq 1:8$ .

### 5.2. Secondary Endpoints

- Persistence of antibodies with respect to components of the investigational vaccine, 2, 3, 4, 5, 6 years after booster vaccination:
  - rSBA-MenA titres  $\geq 1:128$  and GMTs.
  - rSBA-MenC titres  $\geq 1:128$  and GMTs.
  - rSBA-MenW-135 titres  $\geq 1:128$  and GMTs.
  - rSBA-MenY titres  $\geq 1:128$  and GMTs.
  - hSBA-MenA titres  $\geq 1:4$ ,  $\geq 1:8$  and GMTs.
  - hSBA-MenC titres  $\geq 1:4$ ,  $\geq 1:8$  and GMTs.
  - hSBA-MenW-135 titres  $\geq 1:4$ ,  $\geq 1:8$  and GMTs.
  - hSBA-MenY titres  $\geq 1:4$ ,  $\geq 1:8$  and GMTs.
- Serious adverse events:
  - Occurrence of serious adverse events related to vaccination and any event related to lack of vaccine efficacy (ie, meningococcal disease) from the subject's last visit in study MENACWY-TT-048 EXT: 039 Y2, 3, 4, 5 (112036) up to each yearly visit in the current study in a retrospective manner.

## 6. STUDY POPULATION

Several cohorts are defined for the purpose of analyses. The definitions of the cohorts are given as below.

### 6.1. Total Cohort at Month X

The Total Cohort at Month X will include all subjects who received primary vaccination in study MENACWY-TT-039 (109670) and booster vaccination in study MENACWY-TT-048 EXT: 039 Y2, 3, 4, 5 (112036) and came back for visit at Month X. The analysis of persistence at Month X will include all vaccinated subjects for whom data concerning persistence endpoint measures are available at Month X.

### 6.2. According-To-Protocol (ATP) Cohort for Persistence at Month X

The ATP cohort for persistence at Month X will include all evaluable subjects:

- who have received the primary and booster vaccination with MenACWY-TT or *Meningitec* vaccine in studies MENACWY-TT-039 (109670) and MENACWY-TT-048 EXT: 039 Y2, 3, 4, 5 (112036), respectively.
- who have available assay results for at least one tested antigen at Month X.
- who have not received a meningococcal polysaccharide or a meningococcal polysaccharide conjugate vaccine not planned in protocol MENACWY-TT-102 EXT: 048 Y2, 3, 4, 5, 6 (200088) before Month X.
- who do not have a history of meningococcal serogroup A, C, W-135, and Y disease prior to Month X.
- who comply with the blood sampling intervals defined in the protocol for Month X (see [Section 5.5](#) of the protocol).
- who do not have an immune compromising medical condition.
- who have not received any immunosuppressant(s) or other immune-modifying drug(s), immunoglobulins, any blood products, investigational drugs, and/or investigational vaccines.
- who were not excluded from the Booster ATP cohort for immunogenicity or ATP cohort for persistence at Month 60 in the MENACWY-TT-048 EXT: 039 Y2, 3, 4, 5 (112036) study, unless the reason for exclusion was either non-compliance with the protocol-defined serum sampling windows or a lack of availability of immunogenicity results at a previous time point. All the previous elimination will be evaluated on case-by-case basis by the clinician to check for validity at that particular time point.

### 6.3. Adapted ATP Cohort

When presenting different time points, the Adapted ATP cohort will be used to denote that for each time point, the corresponding ATP cohort for immunogenicity/persistence has been used. More specifically the analyses on the pre and post booster time points will be based on the booster ATP cohort for immunogenicity defined in MENACWY-TT-048 while the analyses on Month 12 time point will be based on the ATP cohort for persistence at Month 60 in MENACWY-TT-048 and the analysis on Month 24, 36, 48, 60, 72 time points will be based on the ATP cohort for persistence at Month 24, 36, 48, 60, 72 in MENACWY-TT-102, respectively.

### 6.4. Total Enrolled Cohort

The Total Enrolled cohort will include all the subjects enrolled in the study irrespective of the visit at which they are enrolled.

*For the analysis of persistence, presenting pre and post booster data from study -048 and all time points from study -102, this will include all subjects with immunogenicity result available at respective time point. More specifically, this will include subjects with immunogenicity results available at each time point and belonging to corresponding Total Vaccinated Cohort at Month 60 (study -048) or Total Cohort (studies -048, -and -102) regardless their enrolment in study -102.*

## 7. STATISTICAL METHODS

### 7.1. Analysis of Demographics/Baseline Characteristics

- Demographic characteristics of each study cohort will be tabulated: age (in months, at each study visit, with the range and standard deviation), gender, and geographic ancestry.
- Months since the booster vaccination at the corresponding persistence time point will be calculated by group.
- The distribution of subjects enrolled at each study visit among the study sites will be tabulated as a whole and per group and reason for not attending a visit at each study visit among all subjects who participated in study MENACWY-TT-048 EXT: 039 Y2, 3, 4, 5 (112036) will be summarized.

### 7.2. Analysis of Persistence

Persistence data will be analyzed at Month 24, Month 36, Month 48, Month 60 and Month 72 as soon as results for all individual subjects at each time point are available.

The analysis of persistence will be based on the Adapted ATP cohort.

If for any vaccine group, at any time point, the percentage of subjects with serological results excluded for the corresponding ATP cohort is higher than 5%, a second analysis based on the **Total Enrolled Cohort** will be performed to complement the ATP analysis.

### 7.2.1. Within Group Analysis

For each vaccine group, at each blood sampling time point, for each antigen assessed:

- Geometric mean titres (GMT) with 95% CIs will be tabulated.
- Percentages of subjects with titres above the proposed cut-offs with exact 95% CIs will be calculated.
- The distribution of antibody titres will be tabulated and also presented using reverse cumulative curves.

### 7.2.2. Between Group Analysis

An exploratory evaluation of the differences in the immune response at approximately 24, 36, 48, 60 and 72 months after the booster vaccination will be performed in terms of:

- Differences in the percentage of subjects with rSBA-MenC titres  $\geq 1:8$  and  $\geq 1:128$  between the ACWY-TT group and the MenCCRM group, with their standardized asymptotic 95% CIs.
- Differences in the percentage of subjects with hSBA-MenC titres  $\geq 1:4$  and  $\geq 1:8$  between the ACWY-TT group and the MenCCRM group, with their standardized asymptotic 95% CIs.
- Ratio of GMTs between the ACWY-TT group and the MenCCRM group, with their standardized asymptotic 95% CIs for rSBA-MenC antibody titres and hSBA-MenC antibody titres. This will be performed using an Analysis of Variance (ANOVA) model on the  $\log_{10}$  transformation of the titres using the vaccine group as fixed effect.

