### 7.2.3. Modeling Prediction

In order to complement the descriptive analyses of observed persistence per time point and evaluate the bias that may have occurred due to the loss to follow-up after the vaccination, longitudinal analysis will be performed at the last persistence time point at Month 72.

This analysis will be performed for both the rSBA and hSBA assays in both groups.

This analysis will include all results from pre- and post-booster (Month 48 and Month 49 in study MENACWY-TT-048 (112036)) for subjects belonging to the Booster ATP cohort for immunogenicity, Month 12 (Month 60 in study MENACWY-TT-048 (112036)) for subjects belonging to ATP cohort for persistence at Month 60, Month 24 up to Month 72 (in study MENACWY-TT-102 (200088)) for subjects belonging to ATP cohort for persistence at Month 24 up to Month 72.

A longitudinal model taking into account the group and all available immunogenicity time points from pre-booster timepoint (in study 048) until the last timepoint Month 72 (in study MENACWY-TT-102 (200088)) will be fitted. This model will be primarily aimed at evaluating the selection effect in the group and the time points will be considered as categorical.

For a specific assay, the model will include assay results from a time point provided that these were part of the ATP cohort for that time point. Results below cut-off will be set at half the value of the cut-off. The model will be fitted via the proc mixed procedure according to the following code:

```
Model 1 - Repeated model on all available time points  
PROC MIXED data=sero;  
CLASS group time;  
MODEL log_val = group | time;  
  Repeated time / TYPE=UN SUBJECT=pid;  
  Lsmeans group*time;  
RUN;
```

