### 8.3. Methodology for Computing Confidence Intervals

- All CI computed will be two-sided 95% CI.
- The exact 95% CIs for a proportion within a group will be based on the method by Clopper and Pearson, 1934.
- The standardized asymptotic 95% CI for the group difference in proportions will be based on the method 6 described in paper by Newcombe, 1998.
- The 95% CI for geometric mean titres (GMTs) will be obtained within each group separately. The 95% CI for the mean of log-transformed titre will be first obtained assuming that log-transformed values were normally distributed with unknown variance. The 95% CI for the GMTs will be then obtained by exponential-transformation of the 95% CI for the mean of log-transformed titre.
- The 95% CIs of the group GMT ratios will be computed using an ANOVA model on the logarithm10 transformation of the titres. The ANOVA model will include the vaccine group as fixed effect.

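### The exploratory MenC GMT ratio is planned only from a per-visit, group-only ANOVA; the repeated model already in the SAP could supply a loss-adjusted ratio with a CI, but none is requested

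*SAP*

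**What the plan says.** SAP 7.2.2 plans "An exploratory evaluation of the differences in the immune response at approximately 24, 36, 48, 60 and 72 months after the booster vaccination". One component is the "Ratio of GMTs between the ACWY-TT group and the MenCCRM group, with their standardized asymptotic 95% CIs for rSBA-MenC antibody titres and hSBA-MenC antibody titres". On the method it says: "This will be performed using an Analysis of Variance (ANOVA) model on the" log10 titres. SAP 8.3 repeats that "The 95% CIs of the group GMT ratios will be computed using an ANOVA model" on log10 titres and adds that "The ANOVA model will include the vaccine group as fixed effect". No time term, earlier titre or within-child correlation enters. Protocol 10.6.1.2.3 plans the same analysis.

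The data are those of the visit concerned. SAP 6.3 uses the ATP cohort of each time point, and SAP 8.1 excludes children with a missing result. If more than 5% of children with results fall outside an ATP cohort, SAP 7.2 adds an analysis on the Total Enrolled Cohort, but SAP 6.4 still limits that to children with a result at the time point.

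SAP 7.2.3 separately fits a repeated model to rSBA and hSBA titres from pre-booster to Month 72, in both groups, with group, time and their interaction and an unstructured covariance. Its stated aim is to "evaluate the bias that may have occurred due to the loss to follow-up after the vaccination". The only output statement in the code is "Lsmeans group*time". No group difference and no confidence limits are requested, and nothing links the model to the 7.2.2 ratio.

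**The concern.** The sponsor considered loss-to-follow-up bias worth modelling and built a model containing both groups, yet the planned comparison of the two vaccines does not use it. The ANOVA ratio at a visit is unbiased only if, within each group, the children who are missing have the same titre distribution as those who remain. The repeated model needs a weaker condition: loss may depend on titres already recorded for that assay.

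The documents contain a route by which loss could depend on titre. Under protocol 5.3 and 5.7.6, investigators in this open study receive every child's results at each time point and decide on re-vaccination of non-responders. Under SAP 6.2, an unplanned meningococcal vaccine removes a child from later ATP cohorts. The route could act differently by group, because *Meningitec* covers serogroup C only while the results cover all four serogroups. The documents do not say how often this happens.

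At stake is how the MenC comparison is read at the later visits, where the control group is expected to number about 25.

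**Working it through.** **1. The plan's own numbers.** Protocol 10.3 starts from 206 (ACWY-TT) and 42 (MenCCRM) with about 10% loss per visit. N × 0.9^k for k = 1 to 5:

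| | M24 | M36 | M48 | M60 | M72 |
|---|---|---|---|---|---|
| 206 × 0.9^k | 185.4 | 166.9 | 150.2 | 135.2 | 121.6 |
| Stated | 185 | 167 | 150 | 135 | 121 |
| 42 × 0.9^k | 37.8 | 34.0 | 30.6 | 27.6 | 24.8 |
| Stated | 38 | 34 | 31 | 28 | 25 |

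The figures reproduce. Planned loss by Month 72 is 1 − 121/206 = 41% and 1 − 25/42 = 40%. The size of the booster ATP cohort that feeds the model is not stated, so 206/42 stands in for it. No SD, correlation or precision is given for the ratio, so those below are assumptions.

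**2. Precision if loss is random.** ANOVA variance of the log10 difference: SD²(1/n1 + 1/n2). Repeated model, approximated by one fully observed earlier measure with correlation ρ: SD²[(1 − ρ²)(1/n1 + 1/n2) + ρ²(1/N1 + 1/N2)].

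- Month 72: 1/121 + 1/25 = 0.04826. Baseline: 1/206 + 1/42 = 0.02866.
- At ρ = 0.7: 0.51 × 0.04826 + 0.49 × 0.02866 = 0.03866. SE ratio, model to ANOVA: √(0.03866/0.04826) = 0.895.
- SE ratio at ρ = 0.3, 0.5, 0.7, 0.9: 0.98, 0.95, 0.90, 0.82 at Month 72. At Month 24 it lies between 0.996 (ρ = 0.3) and 0.96 (ρ = 0.9).
- With SD 0.7, the Month 72 95% CI is the ratio multiplied and divided by 2.01 under ANOVA, and by 1.94, 1.87 or 1.77 under the model at ρ = 0.5, 0.7 or 0.9.

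Simulation of all eight time points with equal correlation 0.5, 0.7, 0.85 gave Month 72 SE ratios of 0.93, 0.87, 0.82 (SD 0.8, 300 runs) and 0.90, 0.85, 0.81 (SD 0.7, 500 runs). With correlation decaying at 0.6, 0.7, 0.8 per year they were 0.985, 0.968, 0.945 (1,000 runs).

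**3. Bias if loss depends on the last titre.** Month 72 ratio ACWY-TT/MenCCRM, from simulation; the model is fitted by maximum likelihood with group-by-time means and unstructured covariance.

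| Assumed scenario | Correlation | True | ANOVA | Model |
|---|---|---|---|---|
| MenCCRM only; each SD lower doubles the chance of loss; SD 0.7 | 0.5 / 0.7 / 0.85 | 1.00 | 0.74 / 0.67 / 0.62 | 0.99 to 1.00 |
| Same, with half-cut-off values (about 8% below cut-off at Month 72) | 0.5 / 0.7 / 0.85 | 1.00 | 0.76 / 0.70 / 0.67 | 0.99 / 1.03 / 1.02 |
| MenCCRM only; 40% loss per visit if low, 8% otherwise; SD 0.8 | 0.5 / 0.7 | 1.58 | 0.99 / 0.90 | 1.53 / 1.59 |
| Same rule in both groups; 30% if low, 5% otherwise; SD 0.8 | 0.5 / 0.7 / 0.85 | 2.51 | 2.20 / 2.09 / 1.96 | 2.50 / 2.57 / 2.47 |

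Monte Carlo error in the SD 0.8 rows is about 2% on the ratio (for example 0.176/√300 = 0.010 on the log10 scale). With random loss both estimators are unbiased. In the last row one rule still attenuates the ratio, because it removes more children from the group with lower titres.

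**The case against.** The strongest objection is that the sponsor's plan already exposes the problem. SAP 7.2.1 tabulates observed GMTs for the same group-by-time cells for which Model 1 prints LS means. Selection in MenCCRM alone would appear as a gap between observed and model GMTs in that group only. A reader might infer that selection would go unseen; the documents do not support that. The adjusted point ratio is also ten to the power of the difference between two printed LS means. Because the groups share no children, an approximate CI could be built from their standard errors. What stands is that no planned output presents the adjusted comparison with its CI.

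Second, the ratio is exploratory, and protocol 10.7 calls all analyses descriptive. SAP 8.3 states "All CI computed will be two-sided 95% CI"; there is no test, margin or power target. The primary endpoints are percentages at rSBA ≥1:8 and are untouched. This limits the weight of the point.

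Third, the bias scenarios are chosen. Where many children sit near the cut-off (assumed mean log10 titre 1.0), half-cut-off substitution reduced the ANOVA bias to 0.88 and 0.82 at correlations 0.5 and 0.7. This stands.

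Fourth, the model has its own assumptions. It pools one covariance over groups about 5:1 in size. If within-child correlation differs by vaccine (0.8 versus 0.4, or 0.85 versus 0.3), nominal 95% coverage fell to 93% or 92% without selection, and 92% or 89% with it. This stands too, and is why the model ratio should be supportive and not a replacement.

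**Conclusion.** The point holds as an inexpensive improvement to an exploratory analysis. The only planned MenC GMT ratio assumes loss unrelated to titre within group, and the model built to examine that assumption is not asked for the corresponding contrast. With selection in MenCCRM only, SD 0.7 and about 10% loss per visit, a true Month 72 ratio of 1.00 would be reported as about 0.6 to 0.8, against about 1.0 from the model. Heavy mass below the cut-off brings the ANOVA figure closer to 1.

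Three stronger readings should be resisted. The documents do not show that the ratio in this trial will be biased: they give a route for titre-related loss but not its frequency. They do not support a large gain in precision: the SE reduction at Month 72 is roughly 2% to 20%, depending on a correlation that is not given, and it is almost nil at Month 24. Nor does the model remove all selection bias: it requires data to be missing at random given that assay's recorded titres. If children leave the ATP cohort because of A, W-135 or Y titres, it corrects only the part reflected in their MenC titres.

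**What to change.** In SAP 7.2.3, for rSBA-MenC and hSBA-MenC, add the ACWY-TT minus MenCCRM contrast at Months 24, 36, 48, 60 and 72 with 95% CI, for example by ESTIMATE or LSMESTIMATE statements. An unrestricted DIFF CL on the 2 × 8 = 16 cells would print 16 × 15/2 = 120 pairs per assay, of which five are wanted; if DIFF CL is used, keep only the same-time pairs. Name a small-sample degrees-of-freedom method such as Kenward-Roger, since about 25 control children are expected at Month 72 and the code leaves the default.

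In SAP 7.2.2 add wording such as: *The GMT ratio and 95% CI at each visit will also be obtained from Model 1 by back-transforming the group contrast, and shown beside the ANOVA ratio as a supportive estimate allowing for loss that depends on recorded titres.* Record the addition in SAP Section 10.

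The cost is a few code lines, two sentences and one table, with no new data. The downsides are a second ratio per visit to explain, reliance on missing at random, and a CI that may be somewhat too narrow if within-child correlation differs by vaccine. The last two should be stated with the table.

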### 7.2.3. Modeling Prediction

In order to complement the descriptive analyses of observed persistence per time point and evaluate the bias that may have occurred due to the loss to follow-up after the vaccination, longitudinal analysis will be performed at the last persistence time point at Month 72.

This analysis will be performed for both the rSBA and hSBA assays in both groups.

This analysis will include all results from pre- and post-booster (Month 48 and Month 49 in study MENACWY-TT-048 (112036)) for subjects belonging to the Booster ATP cohort for immunogenicity, Month 12 (Month 60 in study MENACWY-TT-048 (112036)) for subjects belonging to ATP cohort for persistence at Month 60, Month 24 up to Month 72 (in study MENACWY-TT-102 (200088)) for subjects belonging to ATP cohort for persistence at Month 24 up to Month 72.

A longitudinal model taking into account the group and all available immunogenicity time points from pre-booster timepoint (in study 048) until the last timepoint Month 72 (in study MENACWY-TT-102 (200088)) will be fitted. This model will be primarily aimed at evaluating the selection effect in the group and the time points will be considered as categorical.

For a specific assay, the model will include assay results from a time point provided that these were part of the ATP cohort for that time point. Results below cut-off will be set at half the value of the cut-off. The model will be fitted via the proc mixed procedure according to the following code:

```
Model 1 - Repeated model on all available time points  
PROC MIXED data=sero;  
CLASS group time;  
MODEL log_val = group | time;  
  Repeated time / TYPE=UN SUBJECT=pid;  
  Lsmeans group*time;  
RUN;
```

#### 7.2.4. Analysis of Safety

At each persistence time point all reported SAEs related to vaccination and any event related to lack of vaccine efficacy from the subject's last visit in study MENACWY-TT-048 EXT: 039 Y2, 3, 4, 5 (112036) will be described in detail in a retrospective manner.

### 8. STATISTICAL CALCULATIONS

#### 8.1. Derived and Transformed Data

##### Immunogenicity

- For a given subject and a given immunogenicity measurement, missing or non-evaluable measurements will not be replaced. Therefore, an analysis will exclude subjects with missing or non-evaluable measurements for the considered parameter.
- The cut-off value is defined by the laboratory before the analysis and is described in [Section 5.7.3](#) of the protocol.
- A seronegative subject is a subject whose titre is below the cut-off value.
- A seropositive subject is a subject whose titre is greater than or equal to the cut-off value.
- The Geometric Mean Titres (GMTs) calculations are performed by taking the anti- $\log_{10}$  of the mean of the  $\log_{10}$  titre transformations. Antibody titres below the cut-off of the assay will be given an arbitrary value of half the cut-off for the purpose of GMT calculation.

## Safety

At each persistence time point, all reported SAEs related to vaccination and any event related to lack of vaccine efficacy from the subject's last visit in study MENACWY-TT-048 EXT: 039 Y2, 3, 4, 5 (112036) will be described in detail in a retrospective manner.

### 8.2. Data Presentation Description

The following decimal description from the decision rules will be used for the demography, immunogenicity and safety.

Display Table	Parameters	Number of decimal digits
Demographic characteristics	Mean, median age	1
Demographic characteristics	SD (age)	1
rSBA-MenA	GMT	1
rSBA-MenC	GMT	1
rSBA-MenW-135	GMT	1
rSBA-MenY	GMT	1
hSBA-MenA	GMT	1
hSBA-MenC	GMT	1
hSBA-MenW-135	GMT	1
hSBA-MenY	GMT	1
Immunogenicity	Ratio of GMT	2
All summaries	% of count, including LL & UL of CI	1
All summaries	% of difference, including LL & UL of CI	2

